OUTCOME MEASURES	
The primary objective;
 
Investigate whether there is a difference in pain VAS scores at 1-hour after a corticosteroid injection for trigger finger, de Quervains tenosynovitis or carpal tunnel syndrome co-administered with or without local anaesthetic.
 
The secondary objectives;
 
i) Investigate whether there is a difference in pain VAS scores during the 24-hours after a corticosteroid injection for trigger finger, de Quervains tenosynovitis or carpal tunnel syndrome co-administered with or without local anaesthetic.
 
ii) Investigate whether there is a difference in the pain VAS scores at the time of the corticosteroid injection for trigger finger, de Quervains tenosynovitis or carpal tunnel syndrome co-administered with or without local anaesthetic.
 
iii) Investigate the difference in the additional analgesia required and in the functional use of the hand during the first 3 hours following a corticosteroid injection for trigger finger, de Quervains tenosynovitis or carpal tunnel syndrome co-administered with or without local anaesthetic.
 
These outcomes will be determined by assessing patients' pain using a 100mm VAS score before and at time of the injection, and at 5-minutes, 1-hour, 2-hours, 3-hours and 24-hours after the injection. This will be supplemented by questions to determine whether additional analgesia was required and if there was any effect on hand function following the injection. No subgroup analysis will be performed.

POPULATION	Patients attending elective hand and wrist outpatient clinics at the University Hospitals Plymouth NHS Trust with a clinical diagnosis of trigger finger, de Quervains and carpal tunnel syndrome.
ELIGIBILITY	All patients over the age 18 years old with a clinical diagnosis of trigger finger, de Quervains tenosynovitis or carpal tunnel syndrome and who are able to give written informed consent for treatment will be included. Patients will be excluded if they have had previous surgery or corticosteroid injection for the condition being treated at the site considered for injection. A previous corticosteroid injection elsewhere in the hand does not exclude a patient from the trial. Those who are pregnant, breast-feeding or who have a history of hypersensitivity to corticosteroid or local anaesthetic will be excluded.
DURATION	The study will run for a 12-month period or until 100 patients have been recruited to the trial.

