Patients will be randomised using the simple randomisation service provided by Sealed Envelope Ltd. This is an online service that provides random permuted block randomisation, ensuring participants are balanced between the control and treatment group. The physician will use a unique URL and password to randomise patients in A (treatment) or B (control) group.

Patients will receive injections containing one of the two following solutions, delivered under landmarks guidance to treat either; trigger finger, de Quervains tenosynovitis or carpal tunnel. Both combinations are used as part of routine practice for soft tissue corticosteroid injections in the hand and wrist at University Hospital NHS Trust by the local Hand and Wrist surgeons:

- A. 1ml of triamcinolone (40mg/1ml)
- or
- B. 1ml of triamcinolone (40mg/1ml) + 1ml 1% Lidocaine

The registrar will draw up, prepare the treatment in a separate room so that the patient will remain blinded. Neither treatment can be distinguished from one another by their appearance alone.

During the clinic appointment the patient will complete a pain VAS score prior to the injection, for pain experience at the time of the injection and at 5 minutes post injection on the patient assessment record. The pain VAS score of the pain experience during the corticosteroid steroid will be recorded immediately after the procedure. The patient then takes the patient assessment record home to complete further pain VAS scores at; 1-hour, 2-hour, 3-hour and 24-hours following the injection. The timings at which these scores must be recorded will be clearly documented on the patient assessment record by the physician before leaving clinic to help remind the patient. There are three further questions, on the same form; that the patient will be required to answer at 3-hours post injection (Appendix 4).

During the first 3-hours after your steroid injection:

1. Did you take any additional painkillers because of pain at the injection site?

YES Medication: _____

Time taken: _____

NO (go to next question)

2. Did you have any reduction in hand function, below normal, as a result of the injection?

YES please describe your reduction in function:

NO

3. Did you experience any new numbness in your hand, as a result of the injection?

YES

NO

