7. STATISTICS AND DATA ANALYSIS

7.1 DESCRIPTION OF STATISTICAL METHODS

The primary objective;

Investigate whether there is a difference in pain VAS scores at 1-hour after a corticosteroid injection for trigger finger, de Quervains tenosynovitis or carpal tunnel syndrome administered with or without local anaesthetic.

Primary outcome measure of primary objective:

1a) A analysis of the mean change in pain VAS score between 1-hour post injection and baseline pre-injection will be performed. The primary intention will be the use of parametric tests

(Unpaired Students T-test) dependent upon the assessment of score distribution (skewness and kurtosis). Non-parametric testing will be employed if the mean distribution fails tests of normality.

Secondary outcome measures of primary objective:

1b) The effect size at 1-hour post injection will be calculated to measure the significance of the difference between the study and control group.

Mean score at 1-hour in corticosteroid alone group	-	Mean score at 1-hour in corticosteroid and LA group
Standard deviation		

The objectives;

i) Additional sensitivity analysis will be conducted to investigate whether there is a difference in pain VAS scores during the 24-hours after a corticosteroid injection for trigger finger, de Quervains tenosynovitis or carpal tunnel syndrome administered with or without local anaesthetic.

Outcome measure: The cumulative pain in the 24-hour period in both groups will be calculated by using the area under the curve. Multilevel linear regression analysis will be conducted to compare 24 hour pain VAS with injection intervention nested in patient condition.

ii) Additional sensitivity analysis will be conducted to investigate whether there is a difference in the pain VAS scores at the time of the corticosteroid injection for trigger finger, de Quervains tenosynovitis or carpal tunnel syndrome administered with or without local anaesthetic.

Outcome measure: the pain VAS scores in each group at the time of the injection. Multilevel linear regression analysis will be conducted to compare pain VAS with injection intervention nested in patient condition.

iii) Investigate the difference in the additional analgesia required and in the functional use of the hand during the first 3 hours following a corticosteroid injection for trigger finger, de Quervains tenosynovitis or carpal tunnel syndrome administered with or without local anaesthetic.

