Outcome measure: The percentage of patients requiring additional analgesia or who experienced worsening hand function will be determined from the three questions asked in the patient assessment record. The results will be presented as numbers with additional details given in the patients' response, but no statistical analysis will be performed on these results.

No interim or subgroup analysis will be performed.

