7.4 RANDOMISATION

Patients will be randomised using the simple randomisation service provided by Sealed Envelope Ltd (<https://www.sealedenvelope.com>). This is an online service that provides random permuted block randomisation, ensuring participants are balanced between the control and treatment group.

7.5 CRITERIA FOR THE TERMINATION OF THE TRIAL.

Once 100 patients have been recruited and randomised to the trial.

7.6 PROCEDURE FOR ACCOUNTING FOR MISSING, UNUSED, AND SPURIOUS DATA.

A 20% fall out rate has been considered. Participants who have not returned their patient assessment records will not be included in the analysis. Results from partially completed forms will be included for analysis.

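### Objectives i and ii: the model nests the injection in the patient's condition, although the two are crossed, and it does not identify the single arm difference those objectives ask for

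*Combined protocol and SAP*

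**What the plan says.** Section 7.1 gives the model for objective i (pain over 24 hours) as "Multilevel linear regression analysis will be conducted to compare 24 hour pain VAS with injection intervention nested in patient condition". For objective ii (pain at the time of injection) it says "Multilevel linear regression analysis will be conducted to compare pain VAS with injection intervention nested in patient condition". The outcome for objective i is introduced just before: "The cumulative pain in the 24-hour period in both groups will be calculated by using the area under the curve". Section 7.1 labels these analyses as additional sensitivity analyses ("Additional sensitivity analysis will be conducted to investigate whether there is a difference in pain VAS scores during the 24-hours"), while the Study Summary and section 2 list the same questions as secondary objectives. In every place the objective is one comparison, with against without local anaesthetic.

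Allocation is by individual patient. Section 3 says "The physician will use a unique URL and password to randomise patients in A (treatment) or B (control) group", and section 7.4 says of the service "This is an online service that provides random permuted block randomisation, ensuring participants are balanced between the control and treatment group". The two solutions listed in section 3 are the same whichever of the three conditions is treated.

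Section 7.1 ends with "No interim or subgroup analysis will be performed", and the Study Summary says "No subgroup analysis will be performed". The documents do not list the fixed and random terms of the model, name the coefficient that gives the arm difference, or say that the pre-injection VAS enters it.

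**The concern.** A factor is nested in another when its levels differ from one level of the other to the next. Here solutions A and B each occur in trigger finger, de Quervains and carpal tunnel syndrome, so the design is a 2 x 3 crossing. A model that nests the injection in the condition describes a different design. An analyst who follows the text must guess which term answers the objective, and two careful analysts could report different models and intervals from the same data.

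Three condition-specific effects would also amount to a subgroup analysis, which the plan excludes. Separately, neither model is stated to use the pre-injection VAS. Every patient is asked for it, section 1.1 stresses comparison with baseline pain, and the primary analysis uses it through the change score.

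At stake are the precision and reproducibility of two secondary results.

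**Working it through.** **The plan's own figure.** Section 7.2 gives a margin of 20 mm, an SD of 25 mm, 95% power and 41 per arm. At one-sided 0.025 (two-sided 5%, section 7.3):

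n per arm = 2 x (1.960 + 1.645)^2 x 25^2 / 20^2 = 2 x 13.0 x 1.5625 = 40.6, rounded up to 41.

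This reproduces the plan. No figure is given for the models of objectives i and ii.

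**What the wording can mean** (41 per arm, SD 25 mm, equal thirds by condition assumed where a mix is needed):

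1. *Condition and injection-within-condition both random, nothing else.* The only fixed effect is the intercept. Arm appears as a variance component over six cells, so there is no arm estimate or CI.
2. *Fixed arm effects within condition.* Each has SE = 25 x sqrt(2 / (41/3)) = 9.6 mm and a 95% half-width of about 19.0 mm. At a 50/30/20% mix the half-widths are 15.6, 20.1 and 24.6 mm. This can be fitted, but it gives three effects and no overall one.
3. *Fixed arm effect with a random arm-by-condition term.* There is one arm effect, but the variance of that term is estimated from three conditions. If the effect is judged on 2 degrees of freedom, the half-width is 4.30 x 5.52 = 23.8 mm even with no true heterogeneity. The text does not say which degrees of freedom apply; the simulation below uses the normal approximation.
4. *Patients grouped by condition, random condition intercept, fixed arm effect.* SE = 25 x sqrt(2/41) = 5.52 mm, half-width 1.99 x 5.52 = 11.0 mm. This is a sensible model but not the one written, because it is patients and not injections that are nested.

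**Size of the loss, by simulation.** The inputs are 40 patients per arm (100 less 20%) and a residual SD of 25 mm. Section 7.2 states that SD for the sample size, so its use here is an assumption. Between-condition SDs of 0, 4, 8 and 12 mm and condition mixes of 60/15/25% or equal thirds are also assumptions, since neither is in the documents. The 20 mm difference serves only as an example size. Random-effects models were fitted by REML.

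| Model | Median SE of arm effect (mm) | Power for 20 mm |
|---|---|---|
| Condition as fixed factor | 5.6 to 5.7 | 92 to 96% |
| Random condition intercept, fixed arm | 5.5 to 5.6 | not tabulated |
| Condition plus cell-within-condition, fixed arm | 5.6 to 5.9 | about 80 to 93% |
| Six random cells, no condition level, fixed arm | 5.8 to 5.9 at SD 0, 9.8 to 10.1 at SD 12 | 88 to 90% at SD 0, 50 to 51% at SD 12 |

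The 80% end of the third row comes from a run of 250 trials per scenario, so its Monte Carlo error is a few points: sqrt(0.80 x 0.20 / 250) = 2.5 points. The median SE in that row barely rises with the between-condition SD, because the condition level absorbs those differences. In the last row nothing absorbs them, and they pass into the SE of the arm effect.

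**Pre-injection VAS.** SE = 25 x sqrt(2/40) x sqrt(1 - r^2). With r = 0, 0.3, 0.5 and 0.7 this gives 5.59, 5.33, 4.84 and 3.99 mm. The correlations are assumed.

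**The case against.** The strongest reply is that the documents narrow the ambiguity themselves. The objectives ask for one difference, the outcomes are described for the two groups, and subgroup analysis is excluded. On that view three condition-specific effects cannot be meant, *nested* is loose wording, and a sensible statistician would fit a fixed arm effect with condition as a grouping level, at no material loss. Much of this stands. That may well be the intention, and the no-subgroup statements do count against the second reading. But the text still puts the injection, not the patient, inside the condition, and it names no arm coefficient. A reader has to correct the model in order to use it.

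A reader might infer that the plan as written would badly widen the intervals, with the SE rising to about 10 mm and power falling to about 50%. The documents do not support that. Those figures need six random cells with the condition level left out, which is not a nested multilevel model, and a large between-condition SD that the documents do not give. Nor can one say in general that the error is conservative: some readings give no arm estimate at all.

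It is also fair to say that adjusting for pre-injection VAS is a gain in efficiency and not the repair of an error. The remark on baseline pain in section 1.1 concerns interpretation of the MCID, not covariates.

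**Conclusion.** The point holds as a mismatch between model and design in objectives i and ii. The factors are crossed, the plan says nested, and the single arm difference is not identified. That conclusion needs no assumed numbers.

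The likely loss of precision is modest. Under a properly nested model the median SE is almost unchanged, and power for a 20 mm difference falls from 92 to 96% to roughly 80 to 93%. Under a random condition intercept there is no material harm. These figures rest on 80 analysed patients, a residual SD of 25 mm carried over from section 7.2, and assumed condition mixes and between-condition SDs. The documents give no SD for pain at injection or for the 24-hour area under the curve, so the millimetre figures are illustrative for the former and do not transfer directly to the latter.

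The 1-hour primary analysis and the sample size are not affected. This is worth correcting, but it does not threaten the trial's main conclusion.

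**What to change.** In section 7.1, for both objectives, replace the nested multilevel wording by a linear regression of the outcome on arm, with pre-injection VAS and condition (three-level fixed factor) as covariates. The outcome is the 24-hour area under the curve for objective i and the VAS at injection for objective ii. State that the result is the arm coefficient: one pooled difference, corticosteroid alone minus corticosteroid with local anaesthetic, with its 95% CI. Include no arm-by-condition term, in keeping with the exclusion of subgroup analysis.

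The cost is a few lines of text and simpler code. Condition and pre-injection VAS are already part of the planned data, so no new data, visits or patients are needed. The change should be made before the assessment records are opened.

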2. STUDY OBJECTIVES

The primary objective:

Investigate whether there is a difference in pain VAS scores at 1-hour after a corticosteroid injection for trigger finger, de Quervains tenosynovitis or carpal tunnel syndrome co-administered with or without local anaesthetic.

The secondary objectives:

i) Investigate whether there is a difference in pain VAS scores during the 24-hours after a corticosteroid injection for trigger finger, de Quervains tenosynovitis or carpal tunnel syndrome co-administered with or without local anaesthetic.

ii) Investigate whether there is a difference in the pain VAS scores at the time of the corticosteroid injection for trigger finger, de Quervains tenosynovitis or carpal tunnel syndrome co-administered with or without local anaesthetic.

[figure not shown]
iii) Investigate the difference in the additional analgesia required and in the functional use of the hand during the first 3 hours following a corticosteroid injection for trigger finger, de Quervains tenosynovitis or carpal tunnel syndrome co-administered with or without local anaesthetic.

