7.2 THE NUMBER OF PARTICIPANTS

Minimally clinical important difference of 20mm will be used as the clinically admissible margin of non-inferiority. From previous studies, it is assumed to use a standard deviation of 25mm and with a 95% power calculations have determined a required sample size of 41 per study arm, when including a 20% fall out rate a total sample size of 100 patients will be required²².

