7.3 THE LEVEL OF STATISTICAL SIGNIFICANCE

. All statistical testing was done at the two-sided 5% significance level, and 95% CIs with Stata 14.2.

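### Objective iii asks for a between-arm difference in analgesia and hand function, but Section 7.1 plans only counts and percentages, so the precision of any difference could not be judged

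*Combined protocol and SAP*

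**What the plan says.** Section 2 gives secondary objective iii as: "Investigate the difference in the additional analgesia required and in the functional use of the hand during the first 3 hours" after an injection given with or without local anaesthetic. The Study Summary and Section 7.1 repeat it.

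For the outcome measure, Section 7.1 says: "The percentage of patients requiring additional analgesia or who experienced worsening hand function will be determined from the three questions" on the patient assessment record. It continues: "The results will be presented as numbers with additional details given in the patients' response", and closes by ruling that "no statistical analysis will be performed on these results".

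Sections 3 and 3.1 set out the three questions, each answered yes or no at 3 hours: painkillers taken because of pain at the injection site, reduced hand function, and new numbness. The painkiller question also asks which medication was taken and when.

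Section 7.3 sets a general rule for the trial: "two-sided 5% significance level, and 95% CIs with Stata 14.2". It names no method for objective iii.

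**The concern.** The objective is a comparison of the two arms, but the plan for it stops at counts and percentages. It names no effect measure and no interval, and it does not say outright that the percentages will be given by arm. Objectives i and ii each have a regression model in Section 7.1.

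Two things are at stake. First, with about 40 patients per arm, two bare percentages will be read either as a difference or as no difference, and nothing will show how uncertain the comparison is. Section 1.2 argues that local anaesthetic may cause or worsen paraesthesia and interfere with hand use. The function and numbness questions are the trial's evidence on that argument.

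Second, the outcome sentence joins analgesia and worsening function with an 'or' and draws on three questions. It does not say whether each is reported separately. Local anaesthetic could plausibly reduce painkiller use while increasing numbness, and a merged percentage would then hide opposite effects.

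**Working it through.** **1. Comparison of the passages.**

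| Objective | Wording | Planned analysis (Section 7.1) |
|---|---|---|
| i | whether pain scores differ over 24 hours | area under the curve; multilevel linear regression |
| ii | whether pain scores differ at injection | multilevel linear regression |
| iii | the difference in analgesia and hand function | percentages, numbers and free text; statistical analysis excluded |

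The general rule in Section 7.3 does not fill the gap for iii, because Section 7.1 excludes analysis of these results specifically. No other section gives an effect measure or interval for it.

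**2. The plan's own sample size.** Section 7.2 gives these inputs: "Minimally clinical important difference of 20mm will be used as the clinically admissible margin of non-inferiority"; "it is assumed to use a standard deviation of 25mm"; "with a 95% power calculations have determined a required sample size of 41 per study arm". With a two-sided 5% level (one-sided 2.5%) and a true difference of zero:

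n per arm = 2 × SD² × (z₀.₉₇₅ + z₀.₉₅)² / margin² = 2 × 25² × (1.960 + 1.645)² / 20² = 40.6, rounded up to **41**.

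The stated figure reproduces. For drop-out, 82 / 0.8 = 102.5 (103) and 82 × 1.2 = 98.4 (99). The stated total of 100 lies between them. The trial is sized for the 1-hour pain score only, and no figure is stated for objective iii.

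**3. Precision available for objective iii.** The documents give no event rates, so rates of 10% to 50% are an assumption. With the same rate p in both arms, the approximate 95% half-width for a risk difference is

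1.96 × √(2p(1 − p)/n).

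| Assumed rate p | n = 41 per arm | n = 50 per arm (no drop-out) |
|---|---|---|
| 10% | ±13.0 points | ±11.8 |
| 20% | ±17.3 | ±15.7 |
| 30% | ±19.8 | ±18.0 |
| 50% | ±21.6 | ±19.6 |

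For example, at p = 20% and n = 41: 1.96 × √(2 × 0.20 × 0.80 / 41) = 1.96 × 0.0883 = 0.173.

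At 41 per arm, the increase detectable with 80% power (two-sided 5%) from base rates of 10%, 20%, 30% and 50% is about 26, 29, 30 and 29 points. This supports reporting an estimate with an interval rather than a test.

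**4. What a reader would see.** The counts here are assumed. The Newcombe interval combines the Wilson limits (l, u) of the two proportions:

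lower = d − √[(p₁ − l₁)² + (u₂ − p₂)²]; upper = d + √[(u₁ − p₁)² + (p₂ − l₂)²].

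The Wilson limits are 0.181 to 0.454 for 12/40, 0.263 to 0.554 for 16/40 and 0.105 to 0.348 for 8/40.

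- 12/40 v 8/40: d = +10.0 points. Lower: 0.100 − √(0.119² + 0.148²) = −0.090. Upper: 0.100 + √(0.154² + 0.095²) = +0.281. The interval is −9.0 to +28.1.
- 16/40 v 8/40: d = +20.0 points, interval −0.1 to +38.1.

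At 41 per arm, 12 v 8 gives +9.8 points (−8.9 to +27.6) and 16 v 8 gives +19.5 (−0.2 to +37.4). Percentages of 40% and 20% printed alone would read as a doubling, yet the interval just reaches zero.

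**5. Link to the primary outcome.** The primary measure is the change in pain score from baseline to 1 hour. The painkiller question covers 3 hours, so its yes/no answer mixes use before the 1-hour score with use after it. Later use cannot affect that score. The recorded time of use separates the two, but Section 7.1 does not commit to using it in that way.

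**The case against.** The strongest defence is that this is a deliberate, pre-specified choice. The trial is powered only for the 1-hour pain score, and describing unpowered binary secondary outcomes without testing them is legitimate. Objective iii speaks of the difference, not of whether there is one as i and ii do, so a descriptive reading is open. Any reader with the counts by arm could work out an interval. All of this stands against a demand for hypothesis tests. It does not remove the case for printing the estimate and interval, which costs almost nothing and keeps the choice not to test.

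The documents do not support three stronger readings that a reader might infer.

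- *That objective iii cannot be answered.* Percentages by arm would describe an observed difference. The plan does not say 'by arm' outright, but that is the natural reading of a with-versus-without objective. What is missing is the precision.
- *That the plan defines a composite outcome.* The 'or' may simply list two percentages, and the objective itself joins analgesia and function with 'and'. The wording is ambiguous and goes no further than that.
- *That a 3-hour difference in painkiller use would show whether the primary result was masked.* It would not, because it includes use after the 1-hour score. The medication and time recorded on the form are more informative, and Section 7.1 already promises to present the patients' details. A fix that dropped that promise would make the plan worse.

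**Conclusion.** The mismatch is real but limited. Objective iii is worded as a between-arm comparison, and its plan excludes any estimate of the difference or of its uncertainty. An observed difference could be described, but its precision could not be judged from what the plan commits to report. The handling of the three questions also needs one clarifying sentence.

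At 41 per arm the unreported uncertainty is about ±13 to ±22 points. That range rests on assumed event rates of 10% to 50%, equal in the two arms, and on a normal approximation. The example counts are illustrative only. No stated figure in the plan is wrong, and the primary analysis and sample size are unaffected.

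**What to change.** In Section 7.1, objective iii, remove only the closing clause ("no statistical analysis will be performed on these results", with the 'but' before it) and add:

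> For each of the three questions separately (painkillers, reduced function, new numbness), the number and percentage by arm and the risk difference with 95% CI (Newcombe) will be reported as exploratory; no hypothesis test is planned. Using the recorded time of use, the number of patients in each arm who took painkillers before the 1-hour VAS will also be reported.

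Keep the existing commitment to present the details that patients give. The count before 1 hour is included because, of the painkiller use that the question captures, only that part can affect the primary outcome.

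The cost is a few extra lines of output and intervals that will be wide. No new data are needed.
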